Subjects are required to have a structural MRI scan of clinical quality at least once per year at McLean Hospital that is reviewed by a board-certified radiologist or neurologist and a clinical report is generated usually within 2-4 days. If the subject has not received a structural clinical scan in the past year, one will be obtained for the present study. Subjects will not receive more than one structural clinical MRI within a given 12-month period unless a follow-up scan is recommended by the radiologist who reads the scan. Abnormal reports are reviewed by the Clinical Director of the McLean Imaging Center (MIC), [name] and forwarded to the Principal Investigator, in this case, [name], and the designated study physician. If an abnormality is present, the study physician and PI will coordinate the process of contacting the subject so that an appointment can be made to discuss the findings. The MIC Clinical Director may also assist with this process when requested and appropriate. If a follow-up scan is recommended by the radiologist, we will offer the subject a cost-free repeat scan (with contrast if indicated). In all cases we offer a copy both of the clinical report and the MRI scan (on film or cd) to subjects to take to their primary care or other consulting physicians, at no cost.

FMRI, DTI/DKI, and MRS data collected will be processed with software available in the Neuroimaging Center. Echo planar images will be analyzed off line using a semi-automated fMRI data analysis tool and a motion correction algorithm developed on-site at McLean. Measures of signal intensity will be derived by averaging the signal measured in all pixels in each region of interest (ROI) for each time point during the task activation period.

Describe the plan to be followed by the Principal Investigator/study staff for review of adverse events experienced by subjects under his/her care, and when applicable, for review of sponsor safety reports and DSMB reports. Describe the plan for reporting adverse events to the sponsor and the Partners' IRB and, when applicable, for submitting sponsor safety reports and DSMB reports to the Partners' IRBs. When the investigator is also the sponsor of the IND/IDE, include the plan for reporting of adverse events to the FDA and, when applicable, to investigators at other sites.

NOTE: In addition to the adverse event reporting requirements of the sponsor, the principal investigator must follow the Partners Human Research Committee guidelines for Adverse Event Reporting

In the unlikely event that an adverse event occurs, it will be reported by the primary investigator to the Institutional Review Board, and the IRB's guidelines will be followed to ensure adequate reporting and response. All adverse events will be reported to the Partners Healthcare Internal Review Board for their records.

MONITORING AND QUALITY ASSURANCE

Describe the plan to be followed by the principal investigator/study staff to monitor and assure the validity and integrity of the data and adherence to the IRB-approved protocol. Specify who will be responsible for monitoring, and the planned frequency of monitoring. For example, specify who will review the accuracy and completeness of case report form entries, source documents, and informed consent.

NOTE: Regardless of monitoring plans by the sponsor or others, the principal investigator is ultimately responsible for ensuring that the study is conducted at his/her investigative site in accordance with the IRB-approved protocol, and applicable regulations and requirements of the IRB.

Regulatory binders are kept for all studies at McLean Hospital in order to constantly monitor investigations and ensure that all data is collected safely.

The principal investigator will be responsible for monitoring and ensuring the integrity of the data and adherence to the IRB-approved protocol. They will review any questions or concerns regarding data, and will review each signed consent form for the study.

For guidance, refer to the following Partners policies:

Data and Safety Monitoring Plans and Quality Assurance

[https://partnershealthcare-public.sharepoint.com/ClinicalResearch/DSMP in Human Subjects Research.pdf](https://partnershealthcare-public.sharepoint.com/ClinicalResearch/DSMP%20in%20Human%20Subjects%20Research.pdf)

PRIVACY AND CONFIDENTIALITY

Describe methods used to protect the privacy of subjects and maintain confidentiality of data collected. This typically includes such practices as substituting codes for names and/or medical record numbers; removing face sheets or other identifiers from completed surveys/questionnaires; proper disposal of printed computer data; limited access to study data; use of password-protected computer databases; training for research staff on the importance of confidentiality of data, and storing research records in a secure location.

NOTE: Additional measures, such as obtaining a Certificate of Confidentiality, should be considered and are strongly encouraged when the research involves the collection of sensitive data, such as sexual, criminal or illegal behaviors.

Confidentiality of information collected will be maintained with the assignment of an identification number or code, which will be used in place of subject names in all data analyses and reports. Computer systems are located in the Cognitive and Clinical Neuroimaging Core. Keys showing the assignment of identification numbers to subject names will be stored with subject files in room 204 of the Neuroimaging Building under lock and key. All of the data that is collected will be kept for a minimum of seven years once the study has been completed. Only the Principal Investigator, [name], her research staff, and the study collaborators will have access to the data that is collected.

All subjects will be required to give informed consent and must understand all procedures prior to their participation in the study. Subjects are informed of their confidentiality and privacy rights in the informed consent form. To ensure that subjects' rights and safety are protected during the conduct of this research study, subjects consent to the inspection of their medical records by specifically authorized monitors. Such monitoring may be performed by the Human Research Protection Program of McLean Hospital, or by the FDA or other involved federal agency.

Subjects are informed that all the information obtained in this study will be used for research investigational purposes only. Name of subjects will never be publicly disclosed at any time. Subjects will not be identifiable in any publication that may arise from this research.

Subjects will receive a copy of the consent document to keep as well as a copy of the "Partners Healthcare Notice for Use and Sharing of Protected Health Information." Subjects will be informed that this research will be conducted and administered in compliance with all state and federal laws.

SENDING SPECIMENS/DATA TO RESEARCH COLLABORATORS OUTSIDE PARTNERS

Specimens or data collected by Partners investigators will be sent to research collaborators outside Partners, indicate to whom specimens/data will be sent, what information will be sent, and whether the specimens/data will contain identifiers that could be used by the outside collaborators to link the specimens/data to individual subjects.

In some cases, urine samples may be sent to Quest Diagnostics to assess recent illicit substance use. The samples will be labeled with the subject's initials, date of birth, and study ID.

Plasma samples will be sent to [REDACTED] for quantification of endocannabinoid levels pre- and post-treatment. The samples will be labeled with the ID number and visit number (e.g. CBD001-V1).

[REDACTED]

Specifically address whether specimens/data will be stored at collaborating sites outside Partners for future use not described in the protocol. Include whether subjects can withdraw their specimens/data, and how they would do so. When appropriate, submit documentation of IRB approval from the recipient institution.

Specimens will not be stored off-site for future use not described in the protocol.

RECEIVING SPECIMENS/DATA FROM RESEARCH COLLABORATORS OUTSIDE PARTNERS

When specimens or data collected by research collaborators outside Partners will be sent to Partners investigators, indicate from where the specimens/data will be obtained and whether the specimens/data will contain identifiers that could be used by Partners investigators to link the specimens/data to individual subjects. When appropriate, submit documentation of IRB approval and a copy of the IRB-approved consent form from the institution where the specimens/data were collected.

N/A

LITERATURE CITED

Bergamaschi, M.M. et al. (2011). Cannabidiol reduces the anxiety induced by simulated public speaking in treatment-naïve social phobia patients. *Neuropsychopharmacology*, 36, 1219-1226

Campos, A.C. et al. (2008). Involvement of 5HT1A receptors in the anxiolytic-like effects of cannabidiol injected into the dorsolateral periaqueductal gray of rats. *Journal of Psychopharmacology* 199(2), 223-230

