This study is an investigation of 97 subjects who have expressed interest in using CBD for anxiety. Subjects will complete study visits at McLean Hospital. Following a preliminary phone screen and prior to any evaluation, all study subjects will be required to sign a McLean Hospital approved informed consent form that describes all study procedures. The phone screen includes questions related to medical history, substance use history, demographics, and screening questions from the OASIS (see below) to determine whether the subject has anxiety.

Individuals will be assessed at baseline and weekly for four weeks of treatment with compounds administered as sublingual tinctures in a double-blind, randomized procedure: subjects will receive either a full-spectrum high CBD product, a single-compound CBD product, or matched placebo in a 3:1:1 randomization schedule. Each product will be analyzed and verified at an outside lab for safety and potency. Subjects will self-administer 1 ml (10mg/ml) of CBD or placebo sublingually three times daily. At each weekly visit, individuals will complete clinical scales and have a check-in with study staff. Neuropsychological testing will be performed at baseline and the final visit in order to assess cognitive performance. Buccal swabs will be collected for DNA analysis from all participants in the double-blind phase, and a subset of

individuals will complete blood draws at baseline and week 4 in order to assess levels of circulating endocannabinoids. Finally, a subset of individuals will receive an hour-long MRI scan at baseline and the final visit, with both resting state and task-related functional magnetic resonance imaging (fMRI) in each MRI session. In addition, a brief diffusion tensor imaging (DTI) sequence will also be acquired to examine white matter fiber tract integrity, and magnetic resonance spectroscopy (MRS) will be conducted to examine levels of certain metabolites in the brain.

At the investigators' discretion, in order to assess clinical state, participants may complete daily mood ratings either on paper or electronically via REDCap or StudyTrax. Additionally, subjects will be given the option to complete study drug diaries manually (pencil and paper) or via a secure web portal.

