In order to assess the efficacy of the dose chosen for the double-blind study, we will also conduct a small open-label phase I trial of the full-spectrum CBD tincture prior to initiating the double-blind study. This open-label trial will enroll up to 22 participants who are interested in using CBD, and who have anxiety. This trial will determine whether patients derive clinical benefits at the current dosage proposed for the active treatment arm of the double-blind trial. This trial will examine all components of the originally proposed study. During the open-label phase, a subset of participants (up to n=16) will complete an extra visit that includes clinical rating scales and a 2-hour continuous blood draw directly following administration of the tincture in order to assess plasma concentration of CBD over time and correlation with anxiety.

Subjects will be recruited through IRB-approved advertisements and flyers in regions that have approved medical marijuana. Additionally, medical marijuana healthcare facilities throughout New England, including CannaCare, Integr8, MMJ Physician Practice, and others, may also refer interested patients to contact the study recruitment line for further screening. These healthcare groups provide their interested patients who meet for general inclusion criteria with study recruitment materials. The total sample size for the double-blind study is 75 (45 full-spectrum CBD, 15 single-compound CBD, and 15 placebo); up to 15 of each group (45 total) will also complete the MRI scanning protocol. For the open-label trial, the total sample size is 16 (we will enroll up to 22 to ensure 16 completers); up to 16 subjects will complete the MRI scanning protocol.

Inclusion Criteria

- 1) Subject has provided informed consent
- 2) Subject is 18 or older
- 3) Subject is a native English speaker or acquired English prior to age 5
- 4) Subject scores a minimum of 16 on the Beck Anxiety Inventory (BAI) OR a minimum of 11 on the Overall Anxiety Severity and Impairment Scale (OASIS) at the screening/baseline visit or at phone screening if within 2 weeks of the baseline visit

Exclusion Criteria

Subjects will be excluded if they report any of the following:

- 1) Non-native English speakers
- 2) Estimated IQ < 75
- 3) Meets criteria for DSM-V classification of current substance abuse/dependence, a psychotic disorder, bipolar disorder, or an eating disorder

- 4) A history of head injury or loss of consciousness greater than 5 minutes

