A subset of patients in the open-label phase (up to n=16) will complete an optional 6th visit at least one week after completing the open-label phase of the clinical trial. At this visit, an intravenous catheter will be inserted in an antecubital vein for withdrawal of blood samples for subsequent measure of blood CBD and THC levels. The catheter will be inserted 5 to 10 minutes before the sublingual administration of the standard dose of full-spectrum CBD tincture (1mL of 10mg/ml CBD). Blood will be drawn at a maximum rate of 1 mL/min, and five (5) minute samples will be drawn from 5 to 90 minutes after tincture administration and every 10 minutes from 90 to 120 minutes. Quantitative analyses of CBD and THC levels will be performed by gas chromatography. A total of less than 120 mL of whole blood will be drawn on the study day. This method of continuous sampling has been in place and used successfully in [name] laboratory since 1986 (including current approved protocol [REDACTED]).

A subset of patients in the double-blind phase (up to n=75) will complete a blood draw at baseline and week 4. Plasma will be analyzed for circulating levels of endocannabinoids, including: AEA, 2-AG, 2-OG, PEA, and OEA. Levels of cortisol will also be analyzed. Approximately 10ml of whole blood will be drawn into a non-heparinized tube, centrifuged to separate the plasma, flash frozen and transported to [REDACTED]. The samples will be analyzed via mass spectrometry and levels of each endocannabinoid will be assessed pre- and post-CBD treatment.

For the double-blind study, at the end of the baseline visit, eligible subjects will be randomized to either full-spectrum CBD, single-compound CBD, or placebo using a standard 3:1:1 randomization procedure. In the open-label trial, all subjects will be provided with the full-spectrum CBD tincture at the conclusion of the baseline visit. Subjects will be instructed on how to administer the compound in the morning, midday, and evening; they will be instructed how to draw one full dropper of compound, deposit the amount in the dropper under the tongue, hold for 45-60 seconds, then swallow.

For studies involving treatment or diagnosis, provide information about standard of care at Partners (e.g., BWH, MGH) and indicate how the study procedures differ from standard care. Provide information on available alternative treatments, procedures, or methods of diagnosis.

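### An MRI subset of 45 capped at 15 per group does not follow from scanning before a single blinded 3:1:1 randomisation; about 27/9/9 is expected.

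*Combined protocol and SAP*

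**What the plan says.** All but the last two items are in RESEARCH DESIGN AND METHODS.

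- **Arms.** "The total sample size for the double-blind study is 75 (45 full-spectrum CBD, 15 single-compound CBD, and 15 placebo". Allocation is to full-spectrum, single-compound or "matched placebo in a 3:1:1 randomization schedule".
- **MRI subset.** "up to 15 of each group (45 total) will also complete the MRI scanning protocol".
- **Scan times.** "a subset of individuals will receive an hour-long MRI scan at baseline and the final visit". The description of study procedures places the scan among the baseline-visit assessments. The payment schedule in RECRUITMENT PROCEDURES agrees, with scan payments at visits 1 and 5.
- **Randomisation.** "at the end of the baseline visit, eligible subjects will be randomized to either full-spectrum CBD, single-compound CBD, or placebo", by one standard 3:1:1 procedure. Treatment is "administered as sublingual tinctures in a double-blind, randomized procedure".
- **Sample size.** Statistical Approaches at the end of the document gives 85% power, alpha .05 and at least 45 participants for an interaction effect. It does not tie that figure to MRI.

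The documents describe no MRI stratum, no separate ratio for MRI participants, and no one with access to the allocation who decides who is scanned or rescanned.

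**The concern.** The people who have a baseline scan are settled before any of them has an arm. Whatever decides who is scanned (eligibility, willingness, scanner time), a single 3:1:1 list then divides them 3:1:1 in expectation. An equal split is a different outcome, and the plan gives no mechanism that would produce it.

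What is at stake is Specific Aim 3, the imaging aim. The background section promises imaging before and after four weeks of high-CBD compounds compared with placebo. A reader who takes the stated subset at face value expects up to 15 placebo and 15 single-compound participants with paired scans. The design as described leads one to expect about 9 of each. If study staff instead tried to balance the groups during the trial, who completes MRI would come to depend on treatment arm, and the MRI comparison would lose the protection of randomisation.

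**Working it through.** **Inputs.** From the documents: arms 45/15/15, ratio 3:1:1, MRI cap 15 per group with 45 in total, baseline scan before randomisation, alpha .05 and power 85%. The last two are borrowed from the general sample-size statement. Assumed: exactly 45 participants are chosen for MRI without regard to arm, and all complete both scans.

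**1. The plan's own figures.** 75 × (3, 1, 1)/5 = 45/15/15, and 3 × 15 = 45. The arithmetic is internally consistent. With a cap of 15 in each of three groups, 45 can be reached only as 15/15/15.

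**2. Expected split of 45 scanned before allocation.** 45 × (3, 1, 1)/5 = 27/9/9. Against the cap, full-spectrum is 27 − 15 = 12 over and each small arm is 15 − 9 = 6 below.

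**3. Chance spread.** Two models bracket the answer: a random 45 drawn from arms fixed at 45/15/15 (hypergeometric), and independent 3:1:1 assignment of 45 people (binomial or multinomial).

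| Quantity | Arm totals fixed | Independent assignment |
|---|---|---|
| Full-spectrum, central 95% range | 23–31 | 20–33 |
| Each small arm, central 95% range | 6–12 | 4–14 |
| Both small arms at 12 or more | 0.15% | 1.4% |
| Exactly 15/15/15 | 4.4e-10 | 2.7e-5 |

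The last row is C(45,15)/C(75,45) in the first model and C(45,15) × C(30,15) × 0.6^15 × 0.2^30 in the second.

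**4. What 15/15/15 would need.** To expect 15 in a small arm, 15/0.2 = 75 baseline scans are required, that is, everyone. If the share of the 75 who are scanned is 60%, 80% or 100% (assumed range), the expected splits are 27/9/9, 36/12/12 and 45/15/15. All 30 small-arm participants must also pass the MR exclusions and complete both scans. No rate is given. If each does so independently with probability 0.80, 0.90 or 0.95 (assumed), the chance that all 30 do is 0.80^30 = 0.1%, 0.90^30 = 4% or 0.95^30 = 21%. Full-spectrum completers would then have to be held to 15 of 45 by someone who knows the arms.

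**5. If the full-spectrum cap were enforced.** Stopping once full-spectrum reaches 15 gives about 15/0.6 = 25 scanned, expected 15/5/5. This too requires knowledge of the arm counts.

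**6. Effect on precision.** The standard error of a difference, in SD units, is √(1/n₁ + 1/n₂). The detectable difference comes from the noncentral t distribution (85% power, two-sided .05).

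| Comparison | n | SE | Detectable difference |
|---|---|---|---|
| Any pair, equal split | 15 v 15 | 0.365 | 1.13 SD |
| Full-spectrum v placebo | 27 v 9 | 0.385 (+5%) | 1.19 SD |
| Single-compound v placebo | 9 v 9 | 0.471 (+29%) | 1.51 SD |

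**The case against.** **The wording sets a ceiling.** A reader might infer that 15 per group is a target that cannot be met. The documents do not support that. Nine scans in a small arm comply with a limit of 15, and there is no MRI minimum and no MRI power calculation. This stands. What remains is narrower: a total of 45 under that limit forces 15/15/15, and the expected 27 breaks the full-spectrum limit.

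**15/15/15 is not strictly impossible.** The limit applies to those who complete the MRI protocol, and it does not restrict baseline scans to 45. All 75 could be scanned at baseline and full-spectrum rescans then limited. This also stands, but it needs the conditions in step 4. None of them is described, and the text speaks throughout of scanning a subset.

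**The blind.** A reader might infer that the trial's blind will be broken. The documents do not show this. They do not say who holds the allocation, and an unblinded pharmacist or statistician could manage counts without informing participants or raters. The surviving worry is that choosing completers by arm makes MRI completion depend on arm.

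**The loss is uneven.** Full-spectrum v placebo hardly changes (1.13 to 1.19 SD). Only single-compound v placebo worsens materially, and the documents do not name it as an MRI contrast. A two-sample comparison is also simpler than the planned mixed-model ANOVA. Both points are fair, and they limit the consequence without removing the inconsistency.

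**Conclusion.** The point holds in this form: the plan does not say how an MRI subset of 45 with at most 15 per group can arise from scans done before one blinded 3:1:1 randomisation. As described, 45 scanned participants would be expected to split about 27/9/9. That split is an expectation with chance spread (6–12 or 4–14 in each small arm, depending on the model), so it should not be read as a certain result. Exactly 15/15/15 is negligible under either model.

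The conclusion rests on 45 being scanned, on their being chosen without regard to arm, and on no unstated stratification. The detectable differences assume no loss between scans, since the documents give no dropout rate for the double-blind phase, and they use an alpha and power not set for MRI. The consequence is confined to Specific Aim 3 and is mainly a less precise single-compound v placebo comparison. The main clinical comparison in all 75 is unaffected. A stated figure that the design does not deliver should be corrected.

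**What to change.** Keep 3:1:1 for the whole trial and amend the MRI text as follows:

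1. Decide and record MRI participation before randomisation, without regard to arm.
2. Preferably make MRI participation (yes/no) a stratum of the 3:1:1 list. With 45 in the MRI stratum and 30 outside it, the planned splits are 27/9/9 and 18/6/6, which still add up to 45/15/15.
3. Drop the cap of 15 per group and state the subset as about 27/9/9 of 45.
4. State its detectable differences and how they were obtained: about 1.19 SD for full-spectrum v placebo and 1.51 SD for single-compound v placebo (85% power, two-sided .05, two-sample comparison).

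The cost is a wording amendment and a less favourable stated figure, mainly for single-compound v placebo. The stratum needs a revised list. The documents do not give enrolment status; if enrolment is well advanced, items 1, 3 and 4 still apply, with actual counts by arm reported.

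Randomising the MRI stratum 1:1:1 (15/15/15) and the other 30 at 3:1:1 (18/6/6) would equalise the MRI groups. It would also change the whole trial to 33/21/21, remove 12 full-spectrum participants, and oblige every analysis to adjust for the stratum. That is an optional trade-off for the investigators and is not needed for the correction.

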Subjects will meet with the Principal Investigator, a Clinical Neuropsychologist, or a trained Research Assistant at McLean Hospital for five visits (baseline, and four weekly visits throughout the four-week treatment period). A subset of subjects in the open-label phase will also complete an optional 6th visit; this visit will occur after a >1 week washout period after the final (week 4) visit, where they will return to the lab to complete a 2-hour continuous blood draw after administration of the tincture. Subjects will review and sign the approved informed consent form prior to engaging in any study procedures. A structured clinical screening interview (SCID-P or QuickSCID) will be administered, and demographic information, substance abuse/use, and medical histories will also be obtained. Study inclusion/exclusion criteria will be applied, and appropriate subjects will be enrolled and complete the rest of the study visit, which will consist of clinical ratings and quality of life scales, a neuropsychological assessment, a driving simulation task, and an hour-long MRI scan for a subset of eligible individuals. The imaging protocol will include structural and functional imaging techniques, as well as diffusion tensor imaging/diffusion kurtosis imaging and magnetic resonance spectroscopy.

The baseline visit is estimated to take approximately 6-7 hours, and the final study visit is estimated to take approximately 3-4 hours, with the weekly visits in the interim estimated to take approximately 1 hour, for a total of approximately 12-14 hours required to complete all possible visits. The optional 6th visit will take approximately 3 hours to complete. [REDACTED]

[REDACTED] urine samples will be collected at each visit to measure THC and other substance levels throughout the study. Female subjects who enroll in the study will be informed that their sample will also be used to confirm negative pregnancy (HCG) status (QuPID One-Step Pregnancy). A buccal swab sample will also be collected for DNA analysis in the double-blind phase.

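### The optional PK visit specifies no pre-dose blood sample, so the washout is not verified and any starting CBD or THC cannot be subtracted

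*Combined protocol and SAP*

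**What the plan says.** All of this is in the combined protocol and SAP, under Research Design and Methods.

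- **Purpose.** The open-label paragraph describes a "2-hour continuous blood draw directly following administration of the tincture", done "in order to assess plasma concentration of CBD over time and correlation with anxiety". Specific Aims lists PK/PD of the tincture as exploratory. Up to 16 open-label participants take part.
- **Timing of the visit.** The study-procedures text first says "this visit will occur after a >1 week washout period after the final (week 4) visit". The later, detailed description words the interval as one week or longer after the open-label phase is completed.
- **Sampling.** "The catheter will be inserted 5 to 10 minutes before the sublingual administration of the standard dose of full-spectrum CBD tincture". Then "five (5) minute samples will be drawn from 5 to 90 minutes after tincture administration" and "every 10 minutes from 90 to 120 minutes". CBD and THC are both assayed.
- **Volume.** "Blood will be drawn at a maximum rate of 1 mL/min", and "A total of less than 120 mL of whole blood will be drawn on the study day".

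No sample before the dose is listed in any of these descriptions. Statistical Approaches says nothing about how the concentrations will be analysed.

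**The concern.** Participants reach this visit after 28 days of three doses a day, 84 doses in all. The washout has a minimum but no stated maximum, so its length may vary between people. Exclusion 5 tolerates recreational marijuana up to once a month, and the visible text gives no abstinence rule for the washout. A starting plasma level of zero is therefore an assumption for each person.

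Without a time-zero sample that assumption is never tested. If some CBD or THC is present before the dose, every later concentration includes it, and so would any peak or area computed from them. The amount could differ from person to person, which would also disturb comparisons of concentration between people. The catheter is already in the vein, so the measurement is within easy reach.

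**Working it through.** **1. The sampling descriptions side by side.** The open-label paragraph places the draw directly after administration. The first study-procedures paragraph also places it after administration. The detailed description runs from 5 to 120 minutes after the dose. All three are post-dose only.

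**2. The plan's own figure: blood volume below 120 mL.** Inputs: at most 1 mL/min, sampling from 5 to 120 minutes.

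- Continuous draw from minute 5: 1 × (120 − 5) = 115 mL, which is also 17 × 5 + 3 × 10. The stated limit is reproduced.
- Five mL for each of 18 time points (5, 10, …, 90) and 3 later ones (100, 110, 120): 18 × 5 + 3 × 5 = 105 mL.
- A full two hours from minute 0, or 18 × 5 + 3 × 10: 120 mL, which is not below the limit.

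Adding a pre-dose sample to the 115 mL reading: 4 mL gives 119 mL (within the limit); 5 mL gives 120 mL (not within it).

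**3. How much could be left.** The half-life *h* (in days) is an assumption; the documents give none.

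- Share of the end-of-treatment level left after *w* days: 2^(−w/h).
- Residual relative to the rise from one test dose, using a one-compartment model with 84 equal doses 8 hours apart: the sum over i = 0 to 83 of 2^(−(w + i/3)/h).
- Fall of the residual during the two-hour visit: 1 − 2^(−(2/24)/h).
- That fall as a share of the one-dose rise: the day-7 residual ratio times the two-hour fall.

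| Assumed half-life | Left of end-of-treatment level, day 7 | Residual ÷ one-dose rise, day 7 | Same, day 14 | Fall of residual over 2 h | Fall ÷ one-dose rise, day 7 |
|---|---|---|---|---|---|
| 12 h | 0.006% | 0.02% | 0.00% | 10.91% | 0.00% |
| 1 day | 0.8% | 3.8% | 0.03% | 5.61% | 0.2% |
| 1.5 days | 3.9% | 28% | 1.1% | 3.78% | 1.0% |
| 2 days | 8.8% | 81% | 7.2% | 2.85% | 2.3% |
| 3 days | 19.8% | 267% | 53% | 1.91% | 5.1% |
| 5 days | 37.9% | 822% | 311% | 1.15% | 9.4% |

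Example for 2 days at day 7: 2^(−3.5) = 8.8%; the sum is 0.81; the two-hour fall is 2.85%; 0.81 × 2.85% = 2.3%.

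The ratios to a one-dose rise come from a deliberately simple model, with evenly spaced doses and no distribution phase. They may overstate the residual relative to a real single-dose peak. They show the direction and the sensitivity to the half-life, not an estimate.

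**4. What the residual would distort.** A constant added to every concentration in one person leaves that person's correlation with anxiety unchanged. The last column shows that the offset is close to constant over two hours: its drift is 2.3% or less of the one-dose rise up to a 2-day half-life, and 9.4% at 5 days. Levels do shift, so a peak or area would be raised by whatever residual is present. Between people, offsets unrelated to anxiety would tend to weaken a correlation.

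**The case against.** A reader might infer that carry-over cannot be told apart from the test dose, or that the concentrations are biased upward. The documents do not support either. The washout is the design's control for carry-over. What is missing is a check that it worked. With a half-life of about 1 day or less the residual is negligible, and upward bias arises only if a residual or outside intake is actually present.

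It is also tempting to say that the correlation with anxiety is undermined, or that nothing can be recovered afterwards. The first does not hold within a person, as step 4 shows. On the second, the 5-minute sample gives a rough upper bound on the starting level, and a large flat residual would show there. It is only a proxy, because absorption may have begun.

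Three further points limit the concern:

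- Urine is tested for THC and other substances at each visit, which partly covers interim cannabis use. It gives no plasma level to subtract, and CBD is not named.
- Clinical ratings are part of this visit with no timing stated, so a pre-dose rating cannot be called absent.
- Text is blacked out close to the sixth-visit description, and a pre-dose sample mentioned there cannot be ruled out. The visible descriptions are nonetheless consistent in being post-dose only.

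Peak and area under the curve are not named in the documents. They are used here as the usual summaries of concentration over time.

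**Conclusion.** The point holds in a limited form. In the visible text no pre-dose sample is specified, so the washout goes unverified and any residual or outside CBD or THC cannot be subtracted from the post-dose values.

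The size is unknown. It rests entirely on the assumed half-life: at most 0.8% of the end-of-treatment level left at day 7 for 1 day or less, 8.8% at 2 days, 38% at 5 days. A longer actual washout shrinks these figures. The effect would fall on concentration levels and on between-person comparisons, with little on a within-person concentration–anxiety correlation.

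This is a cheap improvement to an exploratory aim in at most 16 open-label participants. It does not touch the randomized comparison.

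**What to change.** - Specify one time-zero sample from the catheter already in place, just before dosing, assayed for CBD and THC.
- Take one of the visit's clinical ratings at the same moment.
- Report concentrations, and any peak or area, both as measured and with the time-zero value subtracted. Report the time-zero values themselves as the check on the washout.
- Reconcile the volume with the stated limit. On the 5-to-120-minute reading at 1 mL/min, 115 mL is already used, so the sample must be under 5 mL or the draw rate below the maximum. If the draw is meant to run the full two hours at 1 mL/min, it reaches 120 mL before any addition, and schedule and limit need reconciling in any case.
- Reconcile the two wordings of the washout, and record each person's actual interval since the last dose.

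The cost is one extra small sample and assay in at most 16 people, with no additional needle stick, plus the volume reconciliation.
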